#### Cohort exclusion criteria

Individuals will be excluded from the cohort for the following:

- Less than 18 years of age.
- Prevalent cancer. Patients with evidence of a history of any cancer (except non-melanoma skin cancer) at cohort entry will be excluded.
- Use of insulin other than 1 prescription for a short-acting insulin in the 19 months prior to the first cohort defining insulin. A period of 19 months is used to allow for an estimated one month supply from any previous insulin prescription, a 6 month grace period, and a 12 month wash-out period.

For the primary new user analysis, evidence of prior cancer or prior surgeries must occur within the 19 months prior to the first prescription for a long-acting insulin in order for the patient to be excluded from the relevant analyses.

In addition, patients may be excluded from specific analyses as described below:

- For breast cancer, women with prophylactic unilateral or bilateral mastectomy at cohort entry will be excluded from the breast cancer analysis.

- For colon cancer, men and women with evidence of complete or subtotal surgical prophylactic removal of the colon will be excluded from the colon cancer analysis.
- For prostate cancer, men with a partial or complete prostatectomy for any reason will be excluded from the prostate cancer analysis.

# Subsequent Instances of New Use

Within each database, patients who satisfy the inclusion and exclusion criteria more than once (i.e., have multiple instances of initiating insulin therapy after a 19-month wash-out period) will be flagged and enumerated (Appendix A, New User Algorithm). In the primary new user analysis, only instances of new use based on the first eligible prescription of glargine or NPH will be included.

### 5.2 Exposures of Interest

The analysis will be based on new users of insulin glargine and new users of human NPH insulin. Patients who use premixed NPH insulin will be included with NPH insulin users in the primary analysis.

In the MedAssurant analyses, the cohorts will be defined as of the second prescription of a long-acting insulin following the first eligible prescription (see Section 5.1 Study Population). The second prescription must occur within 6 months after the first eligible prescription and patients must receive the same type of long-acting insulin (glargine or NPH) at the first and second prescription. Patients with discrepant insulin prescriptions between their 1st and 2nd prescriptions will not be included in the primary analysis but they will be identified for possible inclusion in secondary analyses. In the Ochsner and Partners HealthCare analyses, only one record indicating the start of glargine or NPH will be required to enter the cohort since the electronic medical record databases do not keep a record of every subsequent prescription.

At the first eligible prescription following the cohort entry date, we will determine whether this is an instance of new use based on whether the patient had a prescription for insulin during the 19 months prior to the first eligible script. A 19-month evaluation period ensures that a patient has at least a 12-month insulin-free period prior to entering the new user cohort as it includes time for a 1 month supply following any prior insulin prescription plus a 6-month grace period plus a 12-month washout period. Note that a patient must have at least 19 months of medication data prior to their first prescription for glargine or NPH in order to be evaluated for the new user cohort; for patients with more than 19 months of data, only the latest 19 months of data will be used. Patients without any prescription for insulin during the 19 months prior to the first eligible script, or with only one prescription for a short-acting insulin during this time period, will be considered new users and will be included in the primary analysis.

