# 5.1 Study Population

For the analysis of data from Partners HealthCare System and Ochsner, individuals from their diabetes registries will be eligible to enter the new user cohort on January 1, 2005 (approximately) or later at the time of their first eligible prescription of either insulin glargine or NPH insulin. Diabetes will be defined in the MedAssurant database by having at least 1 diagnostic code (ICD-9 code 250.x) for diabetes during the 18 months prior to or on the date of the first eligible prescription of glargine or NPH insulin. The earliest date when individuals in the MedAssurant database will enter the new user cohort is July 1, 2004. Individuals must have at least 19 months of continuous membership and pharmacy benefits prior to new user cohort entry; if membership is not well defined, a prescription is required in each of four 6-month periods prior to the first eligible prescription. The cohort will be restricted to adults (aged 18 years and older), since the most common cancers rarely occur in children.

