Stopping, switching, augmenting: Because we are interested in potential harm, the primary analysis will be as treated. Therefore, in the primary analysis that compares new users of glargine with new users of NPH, patients stopping the corresponding drug (glargine or NPH), switching to another long-acting insulin (including detemir), or augmenting with another long-acting insulin will be censored at that point in time. Patients who take a premixed analog insulin during follow-up will be treated in a similar manner (i.e. censored at that point in time). Patients who do not refill their insulin prescription within a period equal to the total days of supply (plus a 6 months grace period) will be treated as if they stopped taking insulin at the end of that period (i.e. they will be censored at the last prescription date plus [the days of supply plus 6 months]). If no information on days of supply is available, an informed guess will be made based on the specific study site (i.e., median days of supply).

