# Appendix B Comparison of Analysis Definitions by Data Source

	MGH	Ochsner	Claims
Identifying patients with diabetes	Validated algorithm	Registry	One diagnosis code of 250.x within the one year period prior to the start of NPH/glargine
Exposure definition and Inclusion/exclusion criteria	One record indicating glargine or the glargine comparator was started.  Must be >=18, no history of cancer (except nonmelanoma skin cancer); patients who have had unilateral or bilateral mastectomies, colectomies or prostatectomies (for reasons other than cancer) will be excluded from the analyses of breast, colon and prostate cancer, respectively	One record indicating glargine or the glargine comparator was started.  Must be >=18, no history of cancer (except non-melanoma skin cancer); patients who have had unilateral or bilateral mastectomies, colectomies or prostatectomies (for reasons other than cancer) will be excluded from the analyses of breast, colon and prostate cancer, respectively	Two prescriptions for the same medication within 6 months are required.  Must be >=18, no history of cancer (except nonmelanoma skin cancer); patients who have had unilateral or bilateral mastectomies, colectomies or prostatectomies (for reasons other than cancer) will be excluded from the analyses of breast, colon and prostate cancer, respectively. Evidence of a history of cancer, mastectomy, colectomy or prostatectomy must be present in the 18 month baseline period.

	MGH	Ochsner	Claims
Cancer outcomes	Cancer registry	Cancer registry	Validated algorithm according to Setoguchi et al
Follow-up/censoring primary analysis	Follow-up starts at first record indicated start of glargine/NPH.  Censoring at stopping,	Follow-up starts at first record indicated start of glargine/NPH.  Censoring at stopping,	Start follow-up at second script after exclusion of incident cancer between first and second script.
	switching, augmenting (except short acting insulin), any cancer (except non-melanoma skin cancer), death, end of database, end of eligibility	switching, augmenting (except short acting insulin), any cancer (except non-melanoma skin cancer), death, end of database, end of eligibility	Censoring at stopping, switching, augmenting (except short acting insulin), any cancer (except non-melanoma skin cancer), end of database, end of eligibility

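### At Ochsner and Partners the primary as-treated analysis reads a missing refill record as stopping, although the Protocol says these databases do not record every later prescription

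*Protocol*

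**What the plan says.** - **Record completeness.** Protocol 5.2 drops the second-prescription requirement at Ochsner and Partners "since the electronic medical record databases do not keep a record of every subsequent prescription". In Appendix B, for both sites, "Follow-up starts at first record indicated start of glargine/NPH".
- **Stopping.** Protocol 5.5 makes the primary analysis as treated. "Patients who do not refill their insulin prescription within a period equal to the total days of supply (plus a 6 months grace period") are taken to have stopped and are censored when that period ends. No site is exempted, and Appendix B lists "Censoring at stopping" in both the MGH (Partners) and Ochsner columns.
- **Only allowance.** "If no information on days of supply is available, an informed guess will be made based on the specific study site", with the median given as the example.
- **New use.** The exclusion criteria in 5.1 explain the window: "A period of 19 months is used to allow for an estimated one month supply from any previous insulin prescription, a 6 month grace period". The remaining 12 months are the washout. Section 5.2 adds: "A 19-month evaluation period ensures that a patient has at least a 12-month insulin-free period prior to entering the new user cohort". It limits the look-back to the most recent 19 months. Appendix A, step 2b, also requires the first prescription of record for the primary new user cohort.
- **Data held.** Section 4 describes the Ochsner registry as including claims and pharmacy data, and the Partners record as holding all clinical and utilization data.

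**The concern.** The plan sees that later prescriptions are incompletely recorded at two sites and adapts the entry rule to that. It does not adapt the stopping rule, which depends on the same records. Filling in a median days of supply repairs a missing supply field; it does not repair a missing refill. Where a refill can go unrecorded, absence of a record does not show that the patient stopped.

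At stake is the late follow-up that matters most for a cancer outcome. Patients still on drug would leave the analysis at a false stop date. How long they stay would depend partly on how often an order is re-entered. If re-entry tracks contact with care, which may also affect cancer detection, the censoring is not plainly uninformative. The listed utilization covariates are measured at baseline only.

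The same gap weakens the statement that the 19-month window ensures an insulin-free year, though to a smaller extent.

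**Working it through.** **The plan's own figure.** 1 month supply + 6 months grace + 12 months washout = 19 months. This reproduces.

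**Inputs.** Grace period 6 months (5.5). Follow-up strata 0-<6, 6-<9, 9-<12, 12-<24 and 24+ months (5.6.1). Assumed, because the Protocol gives neither: days of supply of 1 to 3 months, and a probability p that each refill after the first is recorded, independently of the others.

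**Step 1: patient with no later record.** Censoring time = supply + 6 months.
- 1-month supply: 1 + 6 = 7 months
- 2-month supply: 2 + 6 = 8 months
- 3-month supply: 3 + 6 = 9 months

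All fall before month 12, so this patient contributes nothing to the last two strata.

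**Step 2: patient who never stops and refills on time.** False censoring needs a recorded gap longer than supply + 6 months. With monthly refills that means 7 consecutive unrecorded refills among the 23 due before month 24. With 3-monthly refills it means 3 consecutive among 7. Let q = 1 - p, let r be the run length, and let a(n) be the probability of no such run in n refills. Then a(n) = 1 for n < r, and a(n) = p[a(n-1) + q·a(n-2) + ... + q^(r-1)·a(n-r)] for n ≥ r. The wrongly censored share is 1 - a(n).

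By hand for p = 0.50 and a 3-month supply: 81 of the 2^7 = 128 sequences have no run of three, so the share is 47/128 = 0.367. A simulation of 200,000 patients gives the same values as the formula:

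| Share of refills recorded | 1-month supply | 3-month supply |
|---|---|---|
| 10% | 96% | 97% |
| 25% | 59% | 80% |
| 50% | 7% | 37% |
| 75% | 0.1% | 6% |

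**Step 3: look-back.** A continuous user shows no insulin record in 19 months with probability (1 - p)^k, where k = 19 fills (1-month supply) or 6 fills (3-month supply).

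| Share recorded | 1-month supply | 3-month supply |
|---|---|---|
| 10% | 0.90^19 = 14% | 0.90^6 = 53% |
| 25% | 0.75^19 = 0.4% | 0.75^6 = 18% |
| 50% | about 0 | 0.50^6 = 1.6% |
| 75% | about 0 | 0.25^6 = 0.02% |

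**Step 4: regular re-entry.** With one record every 12 months the uncovered gap is 12 - 1 = 11 or 12 - 3 = 9 months. Both exceed 6, so the stopping rule censors at 7 or 9 months, yet the look-back still finds the earlier use. The look-back fails only when recorded gaps exceed 19 months. The stopping rule is therefore the more fragile of the two.

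**The case against.** Several points on the other side stand.

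- Complete records are not needed. Gaps up to supply plus 6 months are tolerated, and section 5.2 says that not every later prescription is kept, not that only one exists. At 75% recording the error is small. Section 4 also describes richer data than section 5.2 does.
- The lagged and ITT analyses are planned at both sites. ITT does escape the problem. The lags do not remove it, because they count from the same false stop date, and the shorter grace periods in Appendix C would worsen it. ITT is ranked only as a sensitivity analysis.
- The stated role of these sites is to explore channeling by BMI and diabetes type. That is a baseline association, which refill-based censoring does not touch.
- The documents give no reason why missing refills should differ between glargine and NPH, so the direction of any bias in the hazard ratio is unknown.

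A reader might infer more than the documents support:

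- **That long-standing users broadly pass as new.** This needs a recorded insulin gap over 19 months, and Appendix A adds the first-prescription-of-record condition.
- **That the membership rules share the fault.** They rest first on enrolment and pharmacy benefits. "if membership is not well defined, a prescription is required in each of four 6-month periods prior to the first eligible prescription" is a fallback, the follow-up counterpart is left to data review, and missing records there would exclude or censor patients rather than admit old users.
- **That the pooled result is contaminated.** Section 5 pools the larger databases. Its later reference to each data source is naturally read within that sentence.
- **That the loss can be measured against the five years quoted for Ochsner.** That figure describes follow-up in the diabetes registry, not time since insulin initiation.

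**Conclusion.** The point holds, within limits. As written, the primary analysis at Ochsner and Partners takes the absence of a refill record as stopping, in databases that the plan itself says omit some later prescriptions. For a patient with no later record the effect is definite: censoring at about 7 to 9 months, given a supply of 1 to 3 months. Across all continuing users the size is unknown. It runs from 0.1-6% wrongly censored before 24 months at 75% recording to 59-80% at 25%, assuming on-time refills recorded independently.

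The damage is to the site-specific as-treated hazard ratios at these two sites, above all after 12 months. The minimum detectable ratios in section 6 use MedAssurant data only and are unaffected. So, on the natural reading of section 5, is the meta-analysis.

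The look-back is a secondary matter: the insulin-free year is not assured with incomplete records, but material failure needs sparse recording.

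**What to change.** 1. In 5.5 and Appendix B, for Ochsner and Partners, censor for exposure only on a recorded discontinuation, switch or augmentation, not on absence of a refill. Report the planned ITT analysis beside this result.
2. At these sites, use any earlier insulin entry in the record to rule out prior use. Reconcile the 19-month limit in 5.2 with the first-prescription-of-record condition in Appendix A, and soften the claim that the window ensures an insulin-free year.
3. Reconcile section 4 with 5.2 on what prescription data each site holds. If Ochsner's pharmacy data prove close to complete, the refill rule could be kept there with that reason stated.

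The cost is wording, plus some misclassified exposed time after stopping that was never recorded. If discontinuations are seldom recorded, the as-treated result will move towards the ITT result, which is why the two should be shown together.

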#### 5.3 Outcomes of Interest

Incident cases of new cancer will be identified from the respective databases. The three primary outcomes correspond to breast, prostate, and colon cancer individually. Only the primary cancer site will be used to determine whether the patient had breast, prostate or colon cancer. The secondary outcome will be all cancers combined excluding non-melanoma skin cancers. The only carcinoma in situ (CIS) cancers that will be included in the primary outcomes are cases of CIS breast cancer. For the analysis of claims data, an algorithm requiring two cancer diagnoses on different dates within a two month period will be required (Setoguchi et al, 2007).

#### 5.4 Covariates

All covariates are defined based on available information within the 12-month period prior to and including the date of the first long-acting insulin prescription. It is important that this time is constant irrespective of the availability of additional data.

The minimum set of covariates includes age, gender, cohort entry date, co-morbidities (e.g., COPD as proxy for smoking), co-medication (including but not limited to other antidiabetic medications), health care system use (number of in- and outpatient encounters, days hospitalized), and screening behavior (especially cancer screening, see table). If available, smoking status, family history of cancer (overall and specific cancers, if available), body mass index, and duration of diabetes are also covariates of interest.

Potential confounders for specific types of cancers include use of hormone therapy and use of oral contraceptives.

Covariates by category are as follows:

#### Demographic and Background Covariates

Gender, age, BMI, blood pressure, race/ethnicity, smoking status at baseline, socioeconomic status, family history of cancer, duration since diabetes diagnosis, type of diabetes

#### Lab Results at Baseline

Glycemic control (HbA1c levels), lipid tests (triglycerides, HDL, LDL and total cholesterol), creatinine, ALT, hemoglobin, microalbumin, microalbumin/creatinine ratio

#### Co-morbidities at Baseline

History of pulmonary infection or COPD, congestive heart failure, renal insufficiency, diabetic retinopathy, diabetic neuropathy

# Pharmacy data

Diabetes medication adherence, use of other medications of interest

# Health care system use

Number of hospitalizations (for any reason), total number of days in the hospital, number of outpatient physician encounters (including same day procedures or surgeries), number of emergency department visits, cancer screenings (mammography, colonoscopies or sigmoidoscopies, PSA, pap smears, fecal occult blood tests), number of lipid assessments, number of ECGs

# 5.5 Baseline and follow-up (time at risk)

Baseline is defined as the 12-month time period up to and including the date of first prescription of glargine or NPH for new users; all covariates will be assessed based on data from this 12-month period. The start of follow-up for Ochsner and Partners HealthCare System patients will be the date of the first prescription. The start of follow-up for new users in the MedAssurant database will be defined for each cohort member as the date of the second prescription for glargine or the glargine comparator insulin. Note that the first and second prescriptions can be for different insulins as long as both insulins reside within the same group (i.e. glargine or NPH,).

The use of the second prescription allows us to remove patients who filled a prescription but were minimally or never exposed to the insulin products of interest. The potential for this kind of exposure misclassification is much smaller given the dispensing of a second prescription. The use of the second prescription as the start of follow-up results in the potential for changes in prescribed type of insulin (see above), covariates, and exclusion criteria. We will ignore changes in covariates because such changes may already be affected by the first prescription. Patients developing cancer between the first and second prescription will be flagged, enumerated, and excluded from the primary analysis.

Follow-up will generally end at: (1) diagnosis of any cancer (except non-melanoma skin cancer) for both overall cancer and specific subgroups, (2) death, (3) a gap of greater than 6 months in either membership or prescription benefits (if membership is not well defined, if no diagnostic code OR no prescription for

more than 6 months during follow-up; a final determination will be made following a review of the data), or (4) the end of the study (date to be determined with individual sites); whichever comes first. In addition, for the analyses on breast, colon, and prostate cancer risk, patient follow-up will be censored when the target organ is removed for a non-cancer related reason.

- For the breast cancer analysis, complete bilateral mastectomy;
- For the colon cancer analysis, removal of colon;
- For the prostate cancer analysis, complete prostatectomy, when done for reasons not related to prostate cancer.

Stopping, switching, augmenting: Because we are interested in potential harm, the primary analysis will be as treated. Therefore, in the primary analysis that compares new users of glargine with new users of NPH, patients stopping the corresponding drug (glargine or NPH), switching to another long-acting insulin (including detemir), or augmenting with another long-acting insulin will be censored at that point in time. Patients who take a premixed analog insulin during follow-up will be treated in a similar manner (i.e. censored at that point in time). Patients who do not refill their insulin prescription within a period equal to the total days of supply (plus a 6 months grace period) will be treated as if they stopped taking insulin at the end of that period (i.e. they will be censored at the last prescription date plus [the days of supply plus 6 months]). If no information on days of supply is available, an informed guess will be made based on the specific study site (i.e., median days of supply).

# 5.6 Statistical Analysis Methods

# 5.6.1. New User Analysis

The new user analysis (Ray 2003) will be based on a defined period of no insulin use prior to the first eligible prescription. To do so, all patients with a prescription of any insulin during the 19 months prior to the first eligible prescription will be excluded. The only exception will be for patients with only one prescription for a short-acting insulin. To allow for treatment titration and therefore better account for early switching, treatment augmentation, and non-chronic use, follow-up will not start at drug initiation but rather at the second prescription after initiation as outlined above. In cases where only one record is necessary to define the cohort (i.e. Ochsner and Partners HealthCare), follow-up will begin at drug initiation.

For the primary analysis, follow-up will start at the time-point defined above for all cohorts. To allow for time-varying hazard ratios (e.g., varying induction periods), we will stratify the follow-up into 0-<6 months, 6-<9 months, 9-<12 months, 12-<24 months, and 24+ months.

Augmentation with short-acting insulin during follow-up will be ignored for the primary analysis but will be described. To do so, time of a first prescription of a short-acting insulin will be ascertained as a separate variable (as well as specific formulation and dose).

The effect of cumulative insulin dose will be addressed by calculating the cumulative insulin dose as of every new prescription and categorizing patients into mutually exclusive categories of cumulative dose (e.g., >0-<=10kU, >10-<=20kU, >20-<=40kU, >40kU). We will categorize cumulative dose based on the long-acting insulin exclusively as well as on long-acting plus short-acting insulin combined. Time at risk for malignancies will start once a patient reaches the corresponding cumulative dose and end once a patient reaches the next cumulative dose level.

In the as treated new user design, follow-up time equals time on treatment since initiation and thus is an indicator of cumulative dose (while being less affected by intermediates). We will therefore also stratify follow-up time (e.g., 0-6, 6-12, 12-24, 24+ months; see above).

To adjust for potential confounding due to channeling between different long-acting insulins, we will estimate the propensity score for glargine initiation (primary analysis) and prevalent glargine use (secondary analyses) vs. glargine comparator initiation/use. In a first step, all covariates defined will be entered into the propensity score. Continuous or ordinal variables will be coded so as to be able to check

model assumptions (e.g., using dummy variables). Specific attention will be given to year of cohort entry because of the dynamics in channeling over time. Using complete cases only, we will empirically define the 10 covariates that are most strongly (Chi-square statistic) associated with channeling. We will then make a decision about whether these 10 covariates are risk factors for cancer based on substantive knowledge. We will then exclude covariates that are not risk factors for cancer. We will then re-estimate the propensity score based on the refined set of covariates. This re-estimated propensity score will be based on complete cases of the reduced set of retained covariates and thus may include more patients than the initial set of cases. Covariates in this re-estimated propensity score will be deemed confounders and we will thus exclude patients with missing values on these confounders to get an unbiased treatment effect estimate. If we lose more than 5% of our patients based on this strategy, we will consider multiple imputation methods of the covariates most strongly contributing to missingness before estimating the propensity score.

In addition, since BMI has the potential to be an important confounder given its association with the risk of breast and colon cancer, we will estimate the association between obesity (BMI >= 30 vs. < 30) and use of glargine vs. the glargine comparator. This estimate, in conjunction with information from the literature on the association between BMI and various cancer outcomes (Renehan et al., 2008) will be used to estimate the extent of potential confounding by unmeasured BMI in our main analyses (i.e. glargine vs. NPH and cancer risk) using a spreadsheet for unmeasured confounders developed by Schneeweiss et al (2005). We will use a cut point of a change in estimate of +/- 10% on the relative risk scale to define "relevant confounding by BMI" (Maldonado & Greenland, 1993).

We will implement the propensity score by stratification (deciles) and inverse probability of treatment weighting (IPTW). Balance of important covariates will be assessed within deciles of the propensity score and in the weighted pseudo population. Any imbalance will be interpreted according to the potential of the imbalanced covariate to affect the risk for the outcome. Given balanced covariates and under the assumption of no unmeasured confounding, incidence rates and survival curves are adjusted or unconfounded and thus can be directly compared. Time trends in absolute and relative hazards will be assessed by stratifying on months of follow-up time (0-6, 6-12, 12-24, 24+). The main measure of association will be the hazard ratio estimated using a Cox proportional hazards model controlling for age and sex as well as any covariates remaining imbalanced after implementation of the propensity score.

